1.2 Rationale

At the half-way point in the Ghana PrenaBelt Trial (“GPT”) (n=41 births in each group), no difference in birth weight was found between the two groups (PrenaBelt versus sham-PrenaBelt) on a two-sample t-test (p=0.51). Conclusions were the same using a non-parametric method (Wilcoxon rank sum test). Note that hypothesis for the GPT is that the birth weights will be higher in the PrenaBelt group than in the sham-PrenaBelt group.

The GPT was originally proposed as a randomized controlled trial with a treatment (PrenaBelt) group and a control (no PrenaBelt) group; however, the Noguchi-IRB strongly recommended that the study be sham-controlled and double blinded. Our team elected to follow the IRB’s recommendation.

In the GPT, participants are educated on the rationale for the study as part of the informed consent process, i.e., back sleep in late pregnancy has been recently implicated as a possibly modifiable risk factor for stillbirth and low birth weight. Participants are subsequently randomized to receive treatment with a PrenaBelt or a sham-PrenaBelt and are blinded to their treatment allocation.

Given the results of the interim analysis, it is questioned if the back-sleep education during the consent process could be having an effect on the sleep behaviour of the participants independently of their treatment allocation. The GPT Team reports that the education could be having an effect, for example, some participants in the sham-PrenaBelt group have reported that they stopped using their assigned device because they had since trained themselves to sleep exclusively on their left side using alternative means.

Many campaigns have had unprecedented impact on public health by education alone, for example, the “back-to-sleep” campaign to prevent sudden infant death syndrome. Therefore, since both the PrenaBelt (treatment) and sham-PrenaBelt (sham-control) groups have received back-sleep education, our team contends that an investigation of a third group without back-sleep education, a true control group, is warranted for comparison.

2 Research Question

What is the mean birth weight and standard deviation of babies born to a cohort of women who:

- Meet the same inclusion/exclusion criteria as the cohort in the Ghana PrenaBelt Trial,
- Have not received education that back sleep during late pregnancy is a possible modifiable risk factor for low birth weight and stillbirth,
- Did not participate in the Ghana PrenaBelt Trial, and

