- Gave birth to their babies in a similar time period (year 2016) as the Ghana PrenaBelt Trial?

3 Aims

To establish a reference birth weight (mean and standard deviation) of babies born to a cohort of women comparable to the cohort in the Ghana PrenaBelt Trial but who have not received back-sleep education, did not participate in the Ghana PrenaBelt Trial, and whose babies were born in a similar time period and weighed on the same newborn scales. This reference birth weight will serve as a control for the Ghana PrenaBelt Trial.

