3.1 Specific Objectives

[figure not shown]
1. Conduct a review of hospital records to confirm the control group participants meet the inclusion/exclusion criteria of the Ghana PrenaBelt Trial and record the:
 - a. Birth weight
 - b. Date of delivery
 - c. Mode of delivery
 - d. Gestational age at delivery
2. Administer a questionnaire to collect demographic, obstetric, and sleep habit data for characterization of the control group and comparison of the control group to the groups (treatment, sham-control) in the Ghana PrenaBelt Trial.

4 Literature Review

In 2009, the World Health Organization reported the global prevalence of stillbirth (SB)

to be 2.6 million (uncertainty range: 2.1-3.8 million), of which 98% occur in low- and middle-income countries (1) – see Figure 1.

[figure not shown]
In addition to the global burden of SB, the global incidence of LBW infants remains a significant public health challenge. Each year, there are over 20 million infants born with LBW, of which 96% occur in low- and middle-income countries with the highest concentrations in Asia and Africa (2) – see Figure 1. Efforts to reduce the incidence of LBW have not been successful in these regions, and thus the incidence has remained largely unchanged (2).

In the Auckland Stillbirth Study (17), the population attributable risk (PAR) for non-left sleep position to SB was found to be 37%, which is greater than the PARs of the three most important modifiable risk factors for SB (obesity, advanced maternal age, and smoking) combined (3). In an African population (18), members of our team ([name], [name])

found that back sleep during pregnancy was an independent predictor of LBW (OR, 5.0; 95% CI, 1.2–20.2; P=0.025) and SB (OR, 8.0; 95% CI, 1.5–43.2; P=0.016), when controlling for covariates maternal age, gestational age, parity, and the presence of pre-eclampsia. Notably, LBW was found to mediate the relationship between back sleep and SB (18). In the Sydney Stillbirth Study (16), the back sleep position was associated with SB (adjusted OR, 6.26; 95% CI, 1.2–34) and the PAR for reported back sleep was 9.88% (95% CI, 5.67-14.1%). Currently, there is much interest (21) and follow up research occurring worldwide (22).

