5.4 Sample Size Determination

A sample size of one-hundred sixty-two (N=162) participants is selected for the KBTH-GIRHL Healthy Birth Weight Study. N=162 is the minimum combined group size for the Ghana PrenaBelt Trial: n=81 treatments plus n=81 sham-controls. The Ghana PrenaBelt Trial sample size was statistically justified (using power of 0.8 and type I error probability of 0.05 and accounting for 20% lost to follow up) based on a previous study in a Ghanaian population by members of our team ([name], [name]) (18) and using the PS Power and Sample Size Program (Version 3.0).

In order to avoid variance bias in comparison of the non-educated (KBTH-GIRHL Healthy Birth Weight Study) group to the back-sleep educated group (Ghana PrenaBelt Trial), the group sizes should be the same; therefore, one-hundred sixty-two (N=162) participants will be included in this study to match the 162 (minimum) participants in the Ghana PrenaBelt Trial. Since this is a cross-sectional study to recruit a control group only, no participants in this study will be lost to follow up; therefore, 162 participants are required in this study.

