Cover Page

Statistical Analysis Plan

Official Title: Korle Bu Teaching Hospital - Global Innovations for Reproductive Health & Life
Healthy Birth Weight Study: A Cross-Section

NTC03062228

Document Date: 20JUL2016

Statistical Analysis Plan

1. Designation of Personnel

All analyses described will be performed by the Project Lead and Co-Investigator, [name], under the supervision of the consulting statistician, [name]. The analyses described will be performed using the R statistical software package (version 3.2.0., “Full of Ingredients”).

2. Outcome measurements

Primary Outcomes:

- Birth weight
- Customized birth weight centile

Secondary outcomes:

- Gestational Age at Delivery
- Small for Gestational Age
- Low Birth Weight
- Sex of Newborn
- Preterm Delivery
- Mode of Delivery

3. Sample size calculation

A sample size of one-hundred sixty-two (N=162) participants is selected for the KBTH-GIRHL Healthy Birth Weight Study. N=162 is the minimum combined group size for the Ghana PrenaBelt Trial (NTC02379728): n=81 treatments plus n=81 sham-controls. The Ghana PrenaBelt Trial sample size was statistically justified (using power of 0.8 and type I error probability of 0.05 and accounting for 20% lost to follow up) based on a previous study in a Ghanaian population by members of our team ([name], [name]) and using the PS Power and Sample Size Program (Version 3.0).

In order to avoid variance bias in comparison of the non-educated (KBTH-GIRHL Healthy Birth Weight Study) group to the back-sleep educated group (Ghana PrenaBelt Trial), the group sizes should be the same; therefore, one-hundred sixty-two (N=162) participants will be included in this study to match the 162 (minimum) participants in the Ghana PrenaBelt Trial. Since this is a cross-sectional study to recruit a control group only, no participants in this study will be lost to follow up; therefore, 162 participants are required in this study.

4. Treatment randomization

Not applicable. This is a cross-sectional study; therefore, no randomization is performed.

5. Interim safety analysis

Not applicable.

6. Analyses at study termination

Descriptive statistics will be employed for collected demographic, obstetric, and sleep habits information from the Data Collection Questionnaire and outcome measures from the Delivery Outcome Form.

Interpretation of the results from this study will be conducted in conjunction with results from the Ghana PrenaBelt Trial as follows:

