- Comparison of groups (back-sleep education, no back-sleep education):
 - For continuous variables, the assumption of normality will be assessed using Q-Q plots and the Anderson-Darling test.
 - If normal, paired t-test will be used for evaluating differences.
 - If non-normal, Wilcoxon signed rank test will be used for evaluating differences.
 - For dichotomous and categorical data, we will evaluate for differences using Chi-squared, Fisher's exact test, or McNemar's test for repeated measurements.
- Note that all analyses will be conducted via the intention-to-treat approach in order to provide unbiased comparisons among treatment groups.

Central quantitative data will be sorted and stored in Microsoft Excel files. Quantitative data analysis will be performed in the R statistical software. We will report the number of participants with missing data.

7. Deviation from outlined statistical plan

All analyses will be performed as outlined above. Any deviation from this plan will only be done so under the guidance of the consulting statistician, [name], who will give written justification for the modification from the protocol. A description of the changes and justification for such will be available to regulatory and ethics authorities.

[name]
Project Lead, Co-Investigator
GIRHL

[name]
Consulting Statistician
Nova Scotia Trauma Program

[name]
Principal Investigator
Korle Bu Teaching Hospital

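### Paired tests are prescribed for every continuous outcome, including both primary outcomes, although the two groups are different women and no pairing is defined

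*SAP*

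**What the plan says.** SAP section 6 and Protocol section 7 compare women who had back-sleep education (the GPT participants) with women who did not (this study's controls). For continuous variables the rule is "If normal, paired t-test will be used for evaluating differences" and "If non-normal, Wilcoxon signed rank test will be used for evaluating differences". No unpaired alternative is offered.

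SAP section 2 names two primary outcomes, birth weight and "Customized birth weight centile". Both are continuous and fall under this rule, as does gestational age at delivery.

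Protocol section 3 (Aims) rules GPT participants out of the control group, which it describes as "a cohort of women comparable to the cohort in the Ghana PrenaBelt Trial but who have not received back-sleep education, did not participate". Protocol section 9.4 recruits them by approaching every recently delivered ward patient until the target number is reached. The only use of the idea of matching is in the sample-size text (Protocol 5.4, SAP 3), where 162 controls are taken "to match the 162 (minimum) participants in the Ghana PrenaBelt Trial".

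**The concern.** A paired t-test and a signed rank test both work on within-pair differences. They need a link between one woman in the first group and one in the second. Here no woman is in both groups and no matching variable or algorithm is given. Equal group sizes do not create pairs.

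The team's own practice points the other way. For the GPT interim comparison of two independent groups, Protocol 1.2 reports a two-sample t-test and a Wilcoxon rank sum test.

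The stake is the inferential use of the study. The protocol's opening summary says that the results, taken with the GPT's, will show whether back-sleep education affects birth weight, and these are the only tests named for that question on continuous outcomes. If the plan is followed as written, two analysts with the same data but different row orders can report different p-values. Under SAP section 7, using the correct test would be a deviation needing written justification, possibly chosen after the data have been seen.

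**Working it through.** **1. Is there a pairing?** Set side by side, the documents give: different women by design (Protocol 2 and 3); consecutive ward recruitment (Protocol 9.4); comparability through shared eligibility criteria, period and scales (Protocol 2, 3 and 5.3); and equal group size, 81 + 81 = 162 (Protocol 5.4, SAP 3). None of these links individuals.

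**2. What an invented pairing does to p.** Inputs: 162 per group (documents); SD 400 to 500 g and differences of 80 to 120 g (assumed, since the documents give neither); two-sided 5% level (assumed). With equal SDs and n = 162:

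- Unpaired: SE = SD × √(2/162) = SD/9, so 450/9 = 50 g. A 99 g difference gives t = 99/50 = 1.98, p = 0.049.
- Paired: t = difference / [SE × √(1 − r)], where r is the sample correlation that the row order happens to create. Under random order r has mean 0 and SD of about 1/√161 = 0.079. For 99 g, r = +0.15 gives t = 1.98/√0.85 = 2.15, p = 0.033; r = −0.15 gives t = 1.98/√1.15 = 1.85, p = 0.067.

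Full range over 10,000 random re-pairings of fixed data:

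| SD (g) | Difference (g) | Unpaired (Welch) p | Paired-t p, range |
|---|---|---|---|
| 400 | 80 | 0.073 | 0.032–0.114 |
| 400 | 120 | 0.007 | 0.002–0.020 |
| 450 | 80 | 0.111 | 0.053–0.155 |
| 450 | 99 | 0.049 | 0.022–0.086 |
| 450 | 120 | 0.017 | 0.005–0.035 |
| 500 | 80 | 0.151 | 0.087–0.209 |
| 500 | 120 | 0.032 | 0.012–0.059 |

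The signed rank test is also unstable. In a separate simulated dataset with a two-sample p of 0.050 and a rank-sum p of 0.116, 2,000 random pairings moved its p from 0.014 to 0.300.

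**3. How often the conclusion changes.** Over 40,000 simulated datasets per setting in arbitrary order (SD 450 g), paired t and Welch disagree on significance in 0.7%, 1.6%, 2.4% and 1.6% of datasets at true differences of 0, 50, 100 and 150 g. Paired-t type I error is 4.9%. Power is almost unchanged: 0.765 paired against 0.768 unpaired at a difference of 0.30 SD.

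**4. If row order is not arbitrary.** The SAP says "Central quantitative data will be sorted and stored in Microsoft Excel files" and gives no sort key. If both files were sorted on a covariate correlated ρ with birth weight and then paired by row, the pairs would correlate at about ρ². The estimated SE would shrink by √(1 − ρ²) while the true SE stayed the same, so type I error ≈ 2 × Φ(−1.96 × √(1 − ρ²)):

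- ρ = 0.3: 2 × Φ(−1.87) = 6.2% (simulated 6.0%)
- ρ = 0.5: 2 × Φ(−1.70) = 9.0% (simulated 9.1%)
- ρ = 0.7: 2 × Φ(−1.40) = 16% (simulated 16%)

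The extreme case, both files sorted on birth weight itself, gives 84% (signed rank 86%).

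**5. Unequal groups.** 162 is a GPT minimum, and Protocol 1.1 gives N = 200. If all 200 had birth weights, pairing would drop 200 − 162 = 38 women, with an SE ratio of √(2/162) / √(1/162 + 1/200) = 0.1111/0.1057 = 1.051, a 5% increase. Protocol 3.1 also plans "comparison of the control group to the groups (treatment, sham-control) in the Ghana PrenaBelt Trial" on questionnaire data. If pairing were carried over to one arm of 81, it would drop 81 controls: √(2/81) / √(1/162 + 1/81) = 0.1571/0.1361 = 1.155, a 15% increase.

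**The case against.** The strongest reply is that little would change in practice. In arbitrary order the paired test holds its size, loses almost no power and rarely disagrees with Welch; the 99 g example was set at the threshold to show the effect. This stands, and it limits the expected harm.

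The formal research question asks only for the control group's mean and SD, which do not depend on the test. This stands too, but the protocol's summary gives the GPT comparison an inferential purpose.

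The sentence about sorting may be routine data handling, and nothing says that the files will be sorted on a relevant variable and joined by row. This is fair: the figures in step 4 show what the plan leaves open, not what is expected, and the verdict does not rest on them.

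No passage orders truncation, and the paired rule sits under the two-group education contrast, not the arm-by-arm comparison. Step 5 is therefore conditional. With unequal groups the fault would probably surface at analysis and be handled as a supervised deviation. That would be a late repair and would leave the plan's text wrong.

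**Conclusion.** The concern holds: the stated tests are wrong for this design and must be corrected. Neither can be run on unlinked women without inventing pairs, and they are the only tests given for continuous outcomes, including both primary outcomes. The fault is an undefined and irreproducible p-value, not automatic inflation of type I error.

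Its size is modest when row order is arbitrary: the conclusion changes only when the result is near the threshold, in roughly 1% to 2% of the simulated datasets. It would be serious only if both files were ordered on birth weight or a variable related to it. The numerical ranges rest on the assumed SD, differences and two-sided 5% level; the absence of pairs rests on the documents alone.

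**What to change.** In SAP section 6 and Protocol section 7:

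- Replace the paired t-test with an unpaired Welch two-sample t-test, reporting the mean difference with its 95% CI.
- Replace the Wilcoxon signed rank test with the Wilcoxon rank-sum test.
- Apply both to birth weight, customized centile and all other continuous variables.
- State that all GPT women with data are used, with no truncation to equal numbers. The sample-size text calls 162 a minimum, but its remark that group sizes should be the same (Protocol 5.4, SAP 3) should be reworded to agree.
- For the comparison with the separate treatment and sham arms, name unpaired methods: Welch ANOVA or Kruskal-Wallis, or each arm against controls.

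Two smaller edits are worth making at the same time: delete McNemar's test, since nothing is measured repeatedly between these groups, and report the mean difference with its CI whatever the normality check shows.

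The cost is wording only, with no new data and no change to N = 162. This corrects the pairing error; it does not adjust for the comparison being non-randomised.
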